Subjects who wish to take part in this study after leaving the STRIDE study (i.e., after their STRIDE FU visit), who participated in Study REN001-101 (UK only), and nDNA-PMM subjects will require additional screening and baseline visits; details of enrolment options are provided in [Section 6.1](#) and [Table 2](#).

The PSOC will assess if nDNA-PMM subjects have the appropriate diagnosis for entry into the study prior to dosing. Subjects who successfully complete screening and are approved by the PSOC will then undergo a Baseline Visit.

After the baseline visit, each subject will have study visits at Months 1, 3, 6, 12, 18, 24, 30, 36, 42 and 48 (and Month 9 and 15 for German subjects). As a final follow-up there will be a telephone call from the study centre to the subject approximately 30 days after the last dose of study drug. A final follow-up telephone call will not be required if mavodelpar has been approved within the country and the subject switches to commercially available medication.

Where the site permits, a concierge service will be available to subjects to arrange hotel accommodation and transport to and from study centre visits and to reimburse any subject study expenses, if applicable. If a study centre requires it, subjects may be asked to have a negative COVID-19 test prior to undertaking scheduled visits at the study centre.

It is expected that most mtDNA-PMM subjects will enrol at the STRIDE Week 24 visit to prevent an interruption in dosing and reduce the number of study assessments. The requirement for screening and baseline visits will be dependent on when the subject enrolls in

the study:

[figure not shown]
- Option 1: Enrolment at the STRIDE Week 24 visit: Most of the STRIDE Week 24 assessments will be regarded as the baseline assessments for this study. Additional assessments will be performed as noted in [Section 6.1.1](#).
- Option 2: Enrolment at the STRIDE FU visit: The STRIDE FU visit will be regarded as the baseline visit for this study with additional assessments performed as noted in [Section 6.1.2](#). If a washout period for any prohibited medication started since the STRIDE Week 24 visit, the subject will exit the STRIDE study and will require additional screening and baseline visits to enter the STRIDE AHEAD Study (Option 3 enroller).

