6.9 Month 24 (Day 672) or Early Withdrawal Visit (Prior to Month 24)

Site staff will provide subjects with meals and snacks at appropriate times during the visit.

If the subject discontinues study treatment prior to Month 24 they will be withdrawn from the study. If they discontinue study treatment between visits, they will be required to attend an early withdrawal visit as soon as possible after their last dose of REN001. If their withdrawal is prior to the Month 24 visit, the below assessments should be carried out:

The following assessments will be carried out:

- The subject should take their study drug with food at their usual dosing time. The actual time of dosing should be recorded by the patient on a dosing card.
- Obtain second morning void urine sample for:
 - Bone marker – NTX
 - Urinalysis and drugs of abuse testing
 - Pregnancy testing (WOCBP)
- Obtain blood samples for:
 - Haematology and biochemistry (including HbA1c)
 - Bone and calcium metabolism markers
 - 2 plasma samples for PK analysis of REN001, sample 1 to be taken on arrival at site, sample 2 to be taken at end of visit. Time of samples to be recorded.
 - FSH test for females (if menopausal symptoms develop)
- Review concomitant medications, non-drug treatments and study drug compliance including capsule counts of remaining study drug.
- Review of AEs.
- Physician completion of subject's PMM phenotypic description.
- Brief physical examination (including weight).
- ECG.
- Vital signs (including temperature).
- PRO Questionnaires (to be completed prior to exercise testing)
 - MFIS
 - PGIS – muscle symptoms and fatigue symptoms
 - PROMIS Short Form – 13a (FACIT Fatigue)
 - SF-36
 - WPAI:SHP
 - PGIC muscle and fatigue symptoms
 - BPI
- 12MWT (to be completed at same time of day as previous visits).
- Eye examination (may be completed \pm 14 days of the visit if required).

- Optional DXA Scan
 - Eligible subjects must have had a DXA scan at baseline, either as part of the STRIDE study or at entry into this long-term safety study. If subject is an Early Withdrawal, a scan will only be performed if there has been at least 20 weeks of dosing following the baseline scan. All female subjects not confirmed as post-menopausal should have an FSH test performed. All WOCBP must have a negative pregnancy test prior to the scan. Where possible, the same scanner should be used at this visit as at the baseline visit. Details can be found in the DXA Manual.

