6.13 Month 48 (Day 1344) or Early Withdrawal Visit (Post Month 24)

Site staff will need to provide subject with meals and snacks at appropriate times during the visit.

If the subject discontinues study treatment prior to Month 48 they will be withdrawn from the study. If they discontinue study treatment between visits, they will be required to attend an early withdrawal visit as soon as possible after their last dose of REN001. If their withdrawal is after the Month 24 visit, the below assessments should be carried out. The following assessments will be carried out:

- The subject should take their study drug with food at their usual dosing time. The time of dosing should be recorded by the patient on a dosing card.
- Obtain second morning void urine sample for:
 - Bone marker – NTX
 - Urinalysis and drugs of abuse

- Pregnancy testing (WOCBP)
- Obtain blood samples for:
 - Haematology and biochemistry
 - Additional bone and calcium metabolism markers
 - FSH test for females (if menopausal symptoms develop)
- Review concomitant medications, non-drug treatments and study drug compliance including capsule counts of remaining study drug.
- Review of AEs.
- Brief physical examination (including weight).
- ECG.
- Vital signs (including temperature).
- PRO Questionnaires:
 - PGIS – muscle symptoms and fatigue symptoms
 - PGIC – muscle symptoms and fatigue symptoms
- Eye examination (may be completed \pm 14 days of the visit if required).
- Optional DXA Scan
 - Eligible subjects must have had a DXA scan at baseline and/or at the Month 24 visit. If subject is an Early Withdrawal after M24, a scan will only be performed if there has been at least 20 weeks of dosing following the M24 scan. All female subjects not confirmed as post-menopausal should have an FSH test performed. All WOCBP must have a negative pregnancy test prior to the scan. Where possible, the same scanner should be used at this visit as at the baseline and Month 24 visits. Details can be found in the DXA Manual.
- Provide home pregnancy testing kit for WOCBP for final pregnancy test prior to the follow-up telephone contact at approximately 30 days after the last dose of study drug.

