8.2. GENERAL METHODS

Continuous variables will be summarized using the number of non-missing observations (n), mean, SD, median, minimum, and maximum. Categorical variables will be summarized using counts and percentages.

Unless otherwise specified, the estimated mean and median for a set of values should be displayed to 1 more decimal place than the original values, and SD should be displayed to 2 more decimal places than the original values. The minimum and maximum should be displayed to the same number of decimal places as the original values. Deviations from this convention may arise to take account of the relevance of the precision (e.g., the distance walked in the 12MWT is reported to the nearest cm, but there is no relevance in presenting the mean to the nearest mm). These deviations from convention will be documented in the relevant analysis sections below.

Percentages will be displayed with 1 decimal place; except percentages will not be presented when the count is zero and 100% will be presented as an integer. Unless stated otherwise, percentages of subjects will be based on the number of subjects with non-missing data in the analysis set used for the presentation.

Unless stated otherwise, an on-treatment measurement will be any measurement collected (including scheduled and unscheduled visits) up to the date of last dose plus one day. Drug interruptions will not be considered, i.e., data will not be excluded during a drug interruption if the subject resumes study treatment; this includes the follow-up period for subjects who enrol in REN001-202 at the REN001-201 FU.

In by-visit summary tables, the baseline will be summarized using all available data, but also for each visit using only the baseline data from subjects with available data at the visit; hence the mean change from baseline will equal the mean observed visit value – mean baseline value.

Throughout this document ‘change from baseline’ refers to the actual change from baseline (i.e., observed visit value – baseline value). The baseline definitions are detailed in [Section 8.6](#).

There will be 3 approaches to summarising the data and, unless stated otherwise, all presentations will be presented for each approach. [Figure 1](#) in [Section 2](#) shows the different pathway options a subject can enter REN001-202 and the 5 distinct reporting groups these

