Subjects who satisfy the criteria for values of potential clinical importance (PCI), identified in the table below, will be summarized and listed. The summary will present the number of subjects with at least one on-treatment post baseline value (including unscheduled visits) satisfying the criteria. The listing will have a similar layout to the overall laboratory listing but will only include those subjects who satisfy the criteria for a specific parameter. The records satisfying the criteria will be identified on the listing. The criteria are:

Category	Parameter	Criteria
Chemistry	Creatine kinase (CK)	Normal baseline value and post $\geq 5 \times$ ULN > ULN baseline value and post $\geq 5 \times$ baseline level
	Aldolase	Normal baseline value and post > ULN
	Troponin I	> ULN
	Potential Hy's Law (ALT, AST, total bilirubin and alkaline phosphatase)	ALT or AST > 3 x ULN and Total bilirubin > 2 x ULN and Alkaline Phosphatase $\leq 2 \times$ ULN

An evaluation of Drug-Induced Serious Hepatotoxicity (eDISH) plot will be generated. The plot will include all post baseline data and will present ALT relative to the upper limit of normal (ULN) on the x-axis and total bilirubin relative to the ULN on the y-axis using a log scale for both axes. Reference lines for Hy's law thresholds, i.e., ALT = 3 x ULN and total bilirubin = 2 x ULN, will be added. The plot will identify group and mutational group and separate plots will be done for on-treatment and off-treatment records.

A spaghetti plot for the changes from baseline in creatine kinase (CK) over time will be presented. The actual sampling day will be used on the x-axis (baseline will be set to day 1). A solid line will be used to connect measurements; however, if the measurement was collected after the last dose of study drug plus one day, then a dotted line will be used. Group will be identified on the plot. The plot will be repeated for aldolase and troponin I. Individual CK, aldolase, ALT, AST and troponin I values relative to the ULN will be plotted over time (i.e., one plot per subject) and group and mutation type will be identified.

The actual sampling day will be used on the x-axis (baseline will be set to day 1). The day of last dose of study drug will be identified on the plot with a vertical reference line.

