12.5. ECG

Observed and change from baseline values will be summarized by visit using descriptive statistics.

A shift table from baseline to visit, for overall ECG interpretation (normal, abnormal not clinically significant, abnormal clinically significant and missing) will be summarised with marginal totals, using counts and percentages.

A shift table from baseline to the maximum post baseline QTcF value will be summarized according to the categories specified in the table below. The maximum will be taken from all scheduled and unscheduled on-treatment values.

Parameter	Criteria
QTcF	
< 450 msec
 
≥ 450 msec and < 480 msec*
 
≥ 480 msec and < 500 msec*
 
≥ 500 msec*

QTcF increase from baseline	
< 30 msec
 
≥ 30 msec and < 60 msec*
 
≥ 60 msec*

* Values of PCI.

Observed and change from baseline values will be listed. The listing will identify QTcF values of PCI (identified in the above table).

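### The laboratory PCI count and the maximum-QTcF shift leave out values taken two or more days after a permanent stop, but keep off-drug values when dosing resumes

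*SAP*

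**What the plan says.** SAP 8.2 sets the default rule: "an on-treatment measurement will be any measurement collected (including scheduled and unscheduled visits) up to the date of last dose plus one day". It then treats interruptions differently: "data will not be excluded during a drug interruption if the subject resumes study treatment". It adds that "this includes the follow-up period for subjects who enrol in REN001-202 at the REN001-201 FU". Neither SAP 8.2 nor Protocol 3.9 limits how long an interruption may last.

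Two safety summaries rest on this definition.

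- SAP 12.2, laboratory PCI criteria for CK, aldolase, troponin I and potential Hy's Law: "The summary will present the number of subjects with at least one on-treatment post baseline value (including unscheduled visits) satisfying the criteria".
- SAP 12.5, shift from baseline to the highest QTcF: "The maximum will be taken from all scheduled and unscheduled on-treatment values".

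On visits, Protocol 3.1 says that "each subject will have study visits at Months 1, 3, 6, 12, 18, 24, 30, 36, 42 and 48", with Months 9 and 15 added in Germany. For subjects who stop early, Protocol 6.13 covers the case "If they discontinue study treatment between visits", and Protocol 6.9 says of the same case that "they will be required to attend an early withdrawal visit as soon as possible after their last dose of REN001". Both forms of the Early Withdrawal visit include haematology, biochemistry and an ECG. No upper limit in days is given, and Protocol 6.14 provides for a visit 21 or more days after the last dose.

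**The concern.** Whether an off-drug value counts depends on what the subject does afterwards. A result obtained ten days after the last dose is dropped if the stop proves permanent and counted if dosing restarts. This holds whatever the drug's half-life.

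The two summaries deliver a secondary safety endpoint for laboratory tests and ECGs: how often changes of potential clinical significance occur (Protocol 3.2.2, SAP 3.2.2). The protocol states no on-treatment limit for it. Adverse events are handled more broadly. Collection runs to about 30 days after the last dose (Protocol 7.1.1.8.1), and the treatment-emergent rule in SAP 12.1 has no end date tied to the last dose.

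Two kinds of value are exposed.

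- **Early Withdrawal samples.** For a subject who stops between visits, these may be the first scheduled laboratory tests and ECG after a long stretch on drug.
- **Liver re-tests after a stop.** Protocol 3.7.2.2 and 3.7.2.3 include criteria based on ALT or AST alone, and Protocol 3.7.2.1 foresees re-testing of ALT, AST, ALP and bilirubin after discontinuation. Bilirubin could first pass 2 x ULN in that re-testing, completing the SAP's potential Hy's Law criterion outside the counted period. This shows a route, not a rate.

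**Working it through.** **1. The rule by day since the last dose (SAP 8.2).**

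| Days after last dose | Permanent stop | Dosing resumes |
|---|---|---|
| 0, 1 | on-treatment | on-treatment |
| 2, 7, 21, 28 | off-treatment | on-treatment |

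The first excluded day is 1 + 1 = 2. An Early Withdrawal visit at 21 days is 21 - 1 = 20 days past the cut-off.

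**2. Visit spacing (target days in Protocol Table 3).** From Day 168 the targets are 336, 504, 672, 840, 1008, 1176 and 1344. Each gap is 168 days, so 7 x 168 = 1176 of 1344 planned days lie in such gaps. In Germany the gaps are 84 days up to Day 504, then 5 x 168 = 840 days. At target spacing, a between-visit stopper may thus have been on drug for up to 168 days since the last scheduled sample. This describes exposure to the problem, not bias.

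**3. Where else an off-treatment value can go.** SAP 8.4 puts it in a visit window if that window holds no on-treatment value. I counted days 2 to 1344 (1343 days), leaving out Months 9 and 15, which SAP 6 keeps out of by-visit summaries.

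- Laboratory windows: 15 + 43 + 43 + 6 x 85 + 43 = 654 days; 654/1343 = 48.7%. The last 43 is the Month 48 window cut at Day 1344.
- ECG windows (no Month 1 ECG): 654 - 15 = 639 days; 639/1343 = 47.6%.
- If each scheduled visit took place on its target day and filled its window, only the days before target remain. For laboratory tests these are 7 + 21 + 21 + 6 x 42 + 42 = 343 days; 343/1343 = 25.5%.

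So an off-treatment value can enter a by-visit table on roughly a quarter to a half of study days. Those tables show normal/low/high for laboratory tests and overall interpretation for ECG. They do not show the CK multiples, the Hy's Law combination or QTcF categories.

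**4. The REN001-201 follow-up visit.** It falls 21 to 28 days after the last dose (SAP Appendix 2), 20 to 27 days past the cut-off. Its laboratory values are on-treatment for subjects who enrol at that visit. They are off-treatment for subjects who enrol after exit or never enrol. The contrast matters only where the visit is post-baseline: from the start of REN001-201, and from the start of REN001 treatment for subjects given mavodelpar in REN001-201. In the REN001-202 presentation the visit is the baseline. No such contrast arises for ECG, because the REN001-201 schedule has no follow-up ECG. Never-enrollers may have few follow-up laboratory values, since footnote 11 links them to Week 24 abnormalities.

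**5. Size, on assumptions.** The documents give no withdrawal rate, visit delay or PCI rate. Take N = 150 + 50 = 200 planned subjects, and assume:

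- w, the proportion withdrawing: 10-40%
- d, the proportion of those seen on day 2 or later: 25-75%
- p, the proportion of those meeting a criterion only at that visit: 2-10%

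The number added is N x w x d x p.

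- Low: 200 x 0.10 x 0.25 x 0.02 = 0.1 subject (0.05 percentage points)
- Middle: 200 x 0.20 x 0.50 x 0.05 = 1.0 subject (0.5 points)
- High: 200 x 0.40 x 0.75 x 0.10 = 6.0 subjects (3.0 points)

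Post-stop re-tests are not in this range.

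**The case against.** The strongest reply is that this is a declared convention and that the SAP separates post-stop data on purpose. The protocol fixes no window for these incidences, so nothing is breached. The values remain visible. In SAP 12.2 the on-treatment limit is attached to the PCI summary, not to the sentence describing the PCI listing. The eDISH plot has an off-treatment version, and the CK, aldolase and troponin I spaghetti plots draw later values as dotted lines. The ECG listing marks QTcF values of potential clinical importance. The affected group is narrow: values sampled on drug, including one that prompts a stop, are counted, and stoppers are asked to attend promptly. A wider window also brings in noise. Protocol 1.4.2.1 says that CK in PMM may reach 30 times ULN after strenuous activity, against a PCI criterion of 5 x ULN or 5 x baseline.

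Most of this stands, and it sets the weight of the point. It also rules out a stronger reading that a reader might infer, namely that late Early Withdrawal samples enter no incidence count at all. The documents do not support that. SAP 8.4 lets them into by-visit shift tables, clinically significant laboratory results are reported as adverse events (Protocol 7.1.2), and Hy's Law cases are handled as SAEs (Protocol 7.1.1.6.1). Nor can one argue from the documents that one day is pharmacologically too short, because they give no half-life.

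What the reply does not answer is that none of these outputs gives a PCI or maximum-QTcF incidence, and that resumption of dosing decides whether an off-drug value counts.

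**Conclusion.** The point holds for two summaries: values from day 2 after a permanent stop enter neither the laboratory PCI count nor the maximum-QTcF shift, while off-drug values before a restart do. The direction is certain. Compared with counting all post-baseline values, the rule gives the same number of subjects or fewer. The size cannot be computed from the documents. It is probably small, because only between-visit stoppers seen on day 2 or later and post-stop re-tests are affected, and the 0.1 to 6 subjects above rest wholly on assumed rates. For a rare finding such as potential Hy's Law, a single subject would still matter to the table. The study is descriptive, with no formal testing, and the values are listed. I rate this as minor: a cheap improvement.

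**What to change.** Keep the existing on-treatment column in SAP 12.2 and 12.5, and leave the by-visit rules as they are. Add the following.

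- A supplementary column counting every post-baseline value from first dose to about 30 days after the final dose, matching adverse event collection. For Group 4a, take the final dose within each participation. Values taken during interruptions stay in, so nothing now counted is lost.
- Beside it, the number of subjects who qualify (or whose QTcF category is higher) only because of values collected more than one day after the most recent dose.
- A listing flag on those values.

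The cost is SAP wording, the extra column with its separate count, and one flag, all from data already collected. The downside is that some late values unrelated to drug, such as exercise-related CK rises, will be counted; the separate count keeps them visible. Local-laboratory results, and samples taken later than about 30 days after the final dose, are still not recovered.
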